## **6.4.2 Secondary Efficacy Assessments**

***All of the individual components of the BICLA will be assessed in different ways as secondary endpoints. These will include:***

1. BICLA response at each month
2. SRI 4 and 5: Response is defined at an endpoint date (EOS and each month vs baseline) The SRI endpoint (7) is defined as a 4 (or 5) point drop in SLEDAI compared to baseline without an increase in BILAG or 10% worsening by PGA.
3. Tender and swollen joint counts (to be analyzed separately and as composite score)
4. Change in SLEDAI scores (EOS and each month vs baseline)
5. Change in PGA scores (EOS and each month vs baseline)
6. Change in BILAG numerical scores (Addition of organ scores where each A=12, B=8, C=1 and D or E=0).
7. Musculoskeletal BILAG response (% with one grade drop and % who reach C or lower)
8. Responder Analysis using the primary endpoint and assessing baseline evidence of (and changes in) a panel of markers selected to identify high levels of IL6/TH17 signalling, and/or B Cell signaling (Erk/Blys). All methods proposed have been previously standardized and are currently available in our laboratory as reviewed above. These will be re-standardized for the current study.

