Accrual Rate: (Number of subjects expected per month)	We expect to enroll 5 patients/month given entry criteria, recruitment track record, and patient appeal of protocol (in particular the early crossover to open label treatment)
FPFV: LPFV: Follow Up:	
 
• FPFV: October 30 2013
 
• LPFV: December 31 2015
 
• Follow Up: April 31 2016
 

Correlative Studies: (PK/PD, etc.)	Extensive exploratory protocol-specific and ancillary immune pharmacodynamic studies, focusing first on changes in IFN alpha, BLyS and other B Cell pathways. A major focus will also be on T Cell pathways with a focus on T suppressor/TH17 dichotomy after treatment with abatacept. A responder analysis will be performed in order to generate hypotheses useful for selecting appropriate patients for this treatment and optimizing dosing strategies.
Inclusion Criteria:	
 
1) Signed Written Informed Consent
 
2) 4 1997 revised ACR Classification Criteria for SLE
 
3) Active polyarticular arthritis meeting at minimum BILAG 2004 B definition with a minimum of 3 tender and 3 swollen joints observed at the screening visit
 
4) Men and women 18 to 70 years of age.
 
5) Women of childbearing potential and men with partners of childbearing potential must use an acceptable method of birth control throughout the study
 
6) Women of childbearing potential must have a negative urine pregnancy test at screening and Study Day 1 (baseline visit) and may not be breast feeding
 

Exclusion Criteria:	
 
1) Current severe disease (e.g. acute nephritis appropriate for induction therapy, CNS lupus (excepting chorea, cranial neuropathy, and resolving optic neuritis) or any lupus condition requiring cyclophosphamide, biologic therapy, or IV bolus steroids of <math>\geq</math> 500 mg.
 
2) Subjects who are incapable of understanding or
 

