The study population will include patients between the ages of 18 and 70 who meet a minimum of 4 1997 revised ACR criteria for SLE and who present with a minimum of 3 tender and 3 swollen joints attributable to lupus arthritis. Patients may have other active manifestations of SLE, and, in the opinion of the investigator, they must be sick enough for intention to treat with a biologic and stable enough for this trial design, which includes withdrawal of any background immune suppressants, to be appropriate.

This study will enroll patients until 60 have completed the protocol through at least the six month point. Randomization will be 1:1 to abatacept or placebo. Approximately 30 patients are expected to complete each arm. At each visit history, physical, and blood tests appropriate to complete the outcome measures will be performed, and adverse event reporting and medication updates will be performed.

Subjects may continue to take nonsteroidal anti-inflammatory medications (including *prn* NSAIDS) and up to 20 mg prednisone (or oral steroid equivalent) daily during the study although steroids will be tapered as tolerated. If the patient is taking an immune suppressant (e.g. antimalarials, mycophenolate mofetil, azathioprine, leflunomide, methotrexate, a calcineurin inhibitor or belimumab) at screening, this must be stopped prior to or on the day of the baseline visit. Patients can elect to receive one or more depomedrol injection(s) up to a total of 320 mg total at the time of the screening visit and/or up to and including the Month 2 visit. Daily oral steroids will be tapered as tolerated if and when the patient begins to improve.

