**2) Target Population:**

Patients with at least 4 1997 revised ACR classification criteria for SLE

Active polyarticular arthritis with a minimum of 3 tender and 3 swollen joints observed at the screening visit and a history consistent with BILAG 2004 “B” arthritis

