### 9.2 Populations for Analyses

**The subject population** As further detailed in the inclusion and exclusion criteria will consist of consecutive consenting lupus patients between ages 18 and 70 who have active polyarticular arthritis characterized by 3 or more tender and 3 or more swollen joints at the screening visit meeting the BILAG 2004 criteria for  $\geq$  B disease (+/- additional evidence of disease activity in other organs).

**The clinical justification** is based on the combination of unmet need in treating a significant, potentially disabling illness, while ensuring a healthy enough population to justify the risks of studying a biologic treatment vs placebo.

**Power Analysis:** Chi Sq or the Fisher's exact test will be used for analysis. The table below has been powered on the assumption that the placebo group will have a result similar to (or even a bit more responsive than) that found in the BOLD study (which was the test prototype for this protocol to determine the safety and feasibility of the statistical assumptions for the placebo study). Data from the BOLD study confirm that there should be a near zero (2.4%) percent response by BICLA at six months in the placebo group in a study with background IS withdrawal. Therefore our assumption of at least 5% response in the placebo group in an identical trial design is reasonable. The second assumption is that the treatment group will have a response rate somewhere between those found in the epratuzumab (by BICLA) and BLISS phase II/III (by SRI) biologic studies e.g. a predicted response rate between 35 and 50%. The most important basis for this assumption, however are the data from patients with lupus arthritis in the Phase II abatacept study, where physicians rated 40% of

the patients treated with abatacept as having “no flare” after baseline. Therefore this expected range by BICLA seems reasonable. (please see power analysis table below which is based on powering the primary endpoint at a range of expected response rates in treatment and placebo groups with a sample size of 60 patients, alpha=0.05).

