## APPENDIX 1: Hybrid SLEDAI with SSFI and PGA

(Circle in SLEDAI Score column if descriptor is present at the time of the visit or in the preceding 4 weeks) (The same instrument can also be used going back only ten days)

Item no.	SLEDAI SCORE	Descriptor	Definition
1	8	Seizure	Recent onset, exclude metabolic, infectious or drug causes
2	8	Psychosis	Altered ability to function in normal activity due to severe disturbance in the perception of reality. Include hallucinations, incoherence, marked loose associations, impoverished thought content, marked illogical thinking, bizarre, disorganized, or catatonic behaviour. Exclude uraemia and drug causes
3	8	Organic brain syndrome	Altered mental function with impaired orientation, memory, or other intellectual function, with rapid onset and fluctuating clinical features, inability to sustain attention to environment, plus at least 2 of the following: perceptual disturbance, incoherent speech, insomnia or daytime drowsiness, or increased or decreased psychomotor activity. Exclude metabolic, infectious or drug causes
4	8	Visual disturbance	Retinal changes of SLE. Include cytoid bodies, retinal hemorrhages, serous exudates or hemorrhages in the choroid, or optic neuritis, scleritis or episcleritis. Exclude hypertension, infection, or drug causes
5	8	Cranial nerve disorder	New onset of sensory or motor neuropathy involving cranial nerves
6	8	Lupus headache	Severe, persistent headache; may be migrainous, but must be non-responsive to narcotic analgesia THIS WOULD RARELY BE ATTRIBUTED TO SLE...ALMOST NEVER SCORED
7	8	CVA	New onset Cerebrovascular accident(s). Exclude arteriosclerosis
8	8	Vasculitis	Ulceration, gangrene, tender finger nodules, periungual infarction, splinter hemorrhages or biopsy or angiogram proof of vasculitis
9	4	Arthritis	> 2 joints with pain and signs of inflammation (i.e. tenderness with swelling or effusion)
10	4	Myositis	Proximal muscle aching/weakness, associated with elevated creatinine phosphokinase (CK)/aldolase, or EMG changes or a biopsy showing myositis
11	4	Urinary casts	Heme-granular or RBC casts
12	4	Hematuria	> 5 RBC/high power field. Exclude stone, infection or other cause
13	4	Proteinuria	> 0.5 gram/24 hours
14	4	Pyuria	> 5 WBC/high power field. Exclude infection
15	2	Rash	Inflammatory type rash
16	2	Alopecia	Abnormal, patchy or diffuse loss of hair

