## ARTHRITIS

*Definition: More than two joints with pain and signs of inflammation, i.e., tenderness, swelling, or effusion.*

Arthritis is scored if it is ongoing; it need not be new or recurrent.

Arthritis is scored only if *more than two* joints manifest signs of inflammation. For example if only the right second and left third PIPs are involved or only both wrists, points for this descriptor are not given.

Inflammation is strictly defined in this activity index as the **presence of tenderness** (the patient complains of pain on palpating the joint or upon going through range of motion) **PLUS** any one of the following:

1. swelling
2. effusion
3. warmth
4. erythema, but must exclude overlying cellulitis

The presence of tenderness alone is not sufficient. A patient's complaints of pain in specific joints without objective findings is not sufficient. An exception would be arthritis of the hip in which case pain in the groin on range of motion accompanied by decreased range of motion in the absence of swelling, warmth, or erythema would be counted.

Inflammation of the tendons, ligaments, bursae, and other periarticular structures are not scored. For example subacromial bursitis and trochanteric bursitis are not scored. If further evaluation reveals osteonecrosis or osteoarthritis, this descriptor is not counted.

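### SRI-5 cannot be met from a baseline SLEDAI of 4, nor SRI-4 from one below 4; entry sets no SLEDAI minimum and the SRI analysis sets take no account of this

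*Combined protocol and SAP*

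**What the plan says.** **Entry.** Section 4.2.1 asks for "Active polyarticular arthritis with a minimum of 3 tender and 3 swollen joints observed at the screening visit", with a history consistent with BILAG B arthritis. The synopsis words it as "Active polyarticular arthritis meeting at minimum BILAG 2004 B definition with a minimum of 3 tender and 3 swollen joints". Activity elsewhere is allowed but not needed: Section 4.1 says "Patients may have other active manifestations of SLE", and Section 9.2 puts a plus-or-minus sign before "additional evidence of disease activity in other organs". SLEDAI is scored at screening and at Treatment Visit 1, but no inclusion or exclusion criterion attaches a threshold to it.

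**Scoring.** Item 9 of the Hybrid SLEDAI in Appendix 1 gives 4 points for more than two "joints with pain and signs of inflammation (i.e. tenderness with swelling or effusion". The Appendix 1 guidelines say each item scores its full points or zero.

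**Endpoint and analysis.** SRI response "is defined as a 4 (or 5) point drop in SLEDAI compared to baseline", provided that BILAG does not increase and PGA does not worsen by 10%. Section 9.4.3 compares SRI response month by month with a chi-square approach. It does not restrict that analysis by baseline SLEDAI, and it does not mention patients who cannot reach the required drop.

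**The concern.** The trial enrols on arthritis, while SRI-5 asks for a fall larger than arthritis alone can supply. A patient with pure lupus arthritis who clears completely goes from 4 to 0 and is recorded as an SRI-5 failure. The same patient can be a BICLA responder, because Section 6.4.1 requires BILAG grade improvement and only that SLEDAI does not rise. Low SRI rates, or an SRI-5 result weaker than BICLA, could then reflect the baseline mix rather than the drug. If the denominator is chosen after the data are seen, the choice is open to challenge.

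**Working it through.** **1. Largest possible fall.** SLEDAI cannot go below 0, so the maximum drop equals the baseline score. The item weights are those in Appendix 1.

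| Baseline pattern | Score = maximum drop | SRI-4 possible | SRI-5 possible |
|---|---|---|---|
| Arthritis only | 4 | yes | no |
| Arthritis + one 1-point item | 5 | yes | yes |
| Arthritis + one 2-point item | 6 | yes | yes |
| Arthritis item not scored, one 2-point item | 2 | no | no |
| Arthritis item not scored, two 2-point items | 4 | yes | no |

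So SRI-4 needs a baseline of at least 4, and SRI-5 at least 5. This step uses only the documents.

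**2. The plan's own figure.** The documents give no expected rate or power for SRI. The nearest figure is the BICLA power table in Section 9.2: 40% versus 5%, 60 patients (30 per arm), alpha 0.05, power 0.86. The two-sided normal approximation with continuity correction reproduces it. The mean rate is 0.225, so the null standard error is √(2 × 0.225 × 0.775 / 30) = 0.1078. The alternative standard error is √((0.40 × 0.60 + 0.05 × 0.95) / 30) = 0.0979. Then (0.35 − 1/30 − 1.96 × 0.1078) / 0.0979 = 1.08, and power is 0.859.

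**3. Dilution.** Let f be the share of each arm below the threshold. Observed rate = (1 − f) × rate in patients able to respond. Two inputs are assumptions: f of 10% to 40%, and SRI rates of 40% versus 5%, borrowed from the BICLA planning range. The full set has 30 per arm and the restricted set 30 × (1 − f). Power is by exact binomial enumeration of the two-sided 0.05 uncorrected chi-square test.

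| f | Observed rates | Difference (points) | Power, 30 per arm | Restricted n per arm | Power, restricted (40% v 5%) |
|---|---|---|---|---|---|
| 0 | 40% v 5% | 35 | 0.943 | 30 | 0.943 |
| 10% | 36% v 4.5% | 31.5 | 0.912 | 27 | 0.929 |
| 20% | 32% v 4% | 28 | 0.871 | 24 | 0.893 |
| 40% | 24% v 3% | 21 | 0.746 | 18 | 0.769 |

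The 0.943 at f = 0 exceeds the plan's 0.86 because this test carries no continuity correction.

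**4. What restriction recovers.** The gains are 0.929 − 0.912 = 0.017, 0.893 − 0.871 = 0.022 and 0.769 − 0.746 = 0.023, about 2 points each. At f = 40%, power falls by 0.943 − 0.746 = 0.197 and restriction returns 0.023. Most of the loss comes from having fewer patients able to respond. The estimated difference, however, returns to 35 points.

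**The case against.** The case against rests on five points.

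- **The share may be small.** One further item, such as rash, low complement, raised DNA binding or a 1-point leukopenia, lifts an arthritis patient to at least 5. Section 4.1 also wants patients ill enough to warrant a biologic. This stands: f cannot be derived from the documents, and one range for both SRI thresholds is only illustrative.
- **Restriction changes the question more than the power.** It estimates the effect in patients able to respond rather than in everyone randomised, and it buys about 2 points under the test that 9.4.3 names. This stands too, and is why the all-randomised rates should stay in view.
- **Other endpoints cover these patients.** BICLA, joint counts, SLEDAI change and musculoskeletal BILAG response are all open to arthritis-only patients, and SRI-4 is reachable from a baseline of 4. True, and it limits the importance, but it does not make SRI-5 interpretable.
- **The denominator is not stated.** Section 9.4.3 does not say that all patients enter the SRI chi-square; the explicit intent-to-treat wording in Section 9 belongs to the primary endpoint. The full denominator is the natural reading, but an inference.
- **Discordant joints.** A reader might infer that a patient with three tender joints and three different swollen joints must score 0 for arthritis and so cannot meet SRI-4. The documents do not support that as a rule. The Appendix 1 guidelines do say "The presence of tenderness alone is not sufficient", but they count pain on movement as tenderness, accept warmth or erythema in place of swelling, and make an exception for the hip. Such a patient may score 0 but need not.

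Nor should the joint entry criterion be tightened on this account. It acts at screening, while SRI is measured from a baseline visit up to a month later with optional steroid injections in between. The 28-day look-back in the SLEDAI guidelines softens that gap but does not guarantee 4 points at baseline.

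**Conclusion.** The point holds in a limited form. It is certain from the scoring rules that baseline SLEDAI 4 rules out SRI-5, that a baseline below 4 rules out SRI-4, and that entry guarantees neither threshold. If the SRI analyses use all randomised patients, both rates and their difference shrink by the factor (1 − f). Under the stated assumptions that takes 35 points to 31.5 at f = 10% and to 21 at f = 40%.

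Two stronger readings should be resisted. One is that the SRI comparison is biased towards an arm: patients who cannot respond are non-responders in both arms, so randomisation leaves only dilution and chance imbalance. The other is that the trial's main conclusion is at risk: BICLA requires no SLEDAI drop, and its power is untouched. This is a cheap improvement to a secondary endpoint.

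**What to change.** In Section 6.4.2 item 2 and Section 9.4.3:

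- define the SRI-4 analysis set as randomised patients with baseline SLEDAI of at least 4, and the SRI-5 set as those with at least 5;
- show the all-randomised SRI-4 and SRI-5 rates alongside;
- report the number of patients per arm below each threshold.

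SLEDAI is already collected at Treatment Visit 1, so no new data are needed. Because the sets depend on a baseline value, the comparison within them stays randomised. The cost is a few lines of analysis text and a somewhat smaller set (27 to 18 per arm if f is 10% to 40%). Leave the joint inclusion criterion as it is.

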**Primary Biologic Endpoint (Which is a secondary endpoint for the trial):**

To test the applicability of baseline imbalance in a.) relative differences in the ratio of *IL6/IL23/IL17* to *Foxp3/TGFβ* (suggesting T Cell signaling imbalance) OR an elevated B cell activation profile to predict clinical response to abatacept either through pre-dose elevation or post-dose reversal of this profile. Based on considerations reviewed in the preliminary data section, the primary biomarker for T

Cell signaling imbalances will be gene expression levels of *IL6/IL23/IL17* and *Foxp3/TGFβ*. The primary biomarker for T Cell signaling-induced B Cell signaling imbalance will be ERK

phosphorylation after cognate interactions between T Cells and the B cell receptor as has been described above.

This will require 8 ml of blood for several cellular response/ stimulation experiments. Follow up samples will be drawn at Month 3 prior to “non-responders” starting new immune suppressant medications, which could confound later biologic assays. This will be repeated at Month 9 to include changes in placebo-treated patients after 3 months on abatacept **respecified Secondary Biologic Analyses**

1. Circulating cytokines of interest (Baseline Month 3 and Month 9) The cytokines to be measured are more easily detected in plasma than in serum. Our Serum Analyte and Biomarker Core has expanded extensive effort in optimizing a 51-plex cytokine assay which is based upon the

BioRad200 platform. Preliminary data from this approach is presented above. This will allow direct testing of select hypotheses, such as abatacept effects on IL-6, IFN alpha, BLyS and TNFRI/II pathways, but also in providing a more exploratory analysis of additional cytokines and chemokines important in T and B cell activation. This method uses a two laser immunobead multiplex technology allowing the levels of 51 cytokines to be monitored with a only 5-8 ml of blood. Serum levels of BLyS and APRIL will also be tested but are unable to be multiplexed based upon features of those analytes.

2. Abatacept Effects Relevant to Other Known B and T Cell Abnormalities of SLE (Baseline Month 3 and Month 9) We hypothesize that efficacy of abatacept will be related to the correction of one or more additional known B or T Cell abnormalities in SLE. We propose to assess response of immune cell subsets to cytokine stimulation or receptor signaling, as well as through basic immunophenotyping, to assess the influence of abatacept on the cells of responders (and potentially non-responders).
3. Effects of Abatacept on B Cell/T Cell gene expression (Baseline Month 3 and Month 9) Prespecified Analysis to determine whether select aspects of gene expression profiling by either microarray analyses or RNAseq (and changes after dosing) can be fit to abatacept pharmacodynamics and efficacy. BLyS, interferon alpha pathway expression, ICOS signaling panel will be primary candidates for further analysis.
4. Ig production by B cells (All Visits). These will be monitored throughout the study

## Other Assessments: Optional Exploratory Analyses

1. Cytokine induction assay (Baseline, Month 3 and Month 9): Induced production of cytokines will be measured in the supernatants of cultured (stimulated T or B cells) using multiplex technology.
2. Functional studies (Baseline, Month 3 and Month 9) will be performed as sample size allows including:a. Calcium concentration in cells stimulated with anti-CD3, b. Protein tyrosine phosphorylation, c. Intracellular IL-2, IL17, STAT3, d. Levels of kinases (Syk and CaMKIV) e. Levels of pERM and ROCK

**Expected results:** Abatacept should affect function of both T and B cells and several abnormalities –outlined above and routinely studied in our labs- will be corrected. The

correction sequence will illuminate mechanism of action of abatacept (beyond the known blockade of costimulation) and focus future efforts at developing pharmacodynamic markers.

**Exploratory Clinical Correlative Studies:** We propose to test the sensitivity and specificity of several lupus quality of life outcome measures and a physician-friendly treat to target system for clinical improvement and biologic changes. The primary clinical and biologic endpoints will be used as the standard comparators. The patient reported outcomes included will be the SF-36, (widely used in SLE trials) and the Lupus PRO (27-29 from original application), none of which have been directly compared against efficacy endpoints.

**Exploratory Biologic Studies:** Serum, plasma, urine, RNA, DNA and buffy coats will be saved and stored. Correlative studies will be performed using samples stored for use by BMS

scientists. Appendix 3, Appendix 4 and Appendix 5 describe ancillary studies to be performed by [name] of Exagen Inc, [name] of Yale University and Drs [name] and [name] of Harvard Medical School. Appendix 6 will update any additional studies to be performed at BMS, and will be submitted to the IRB as an addendum.

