### **6.4.1 Primary Efficacy Assessment: BICLA Response**

BICLA stands for BILAG-based Combined Lupus Assessment. The BILAG refers to the British Isles Lupus Assessment Group Index. We will be using the version known as BILAG 2004 (37). This consists of 97 descriptors for signs and symptoms of lupus divided into 9 organ systems (see appendices for case report forms). Each organ system receives a rating of A (severe disease activity), B (moderate disease activity) C (mild disease activity) D (no disease activity in an organ previously affected) or E (organ inactive and never previously active). These ratings are derived from assessments made on each descriptor within each organ and the determination of whether activity is not present, improving, same, worsening or new/recurrent when comparing the degree of disease activity during the past month to the previous month.

The BICLA (8) includes scores from the BILAG, the SLEDAI and the PGA. The SLEDAI which will be used is the hybrid SLEDAI which incorporates components of two SLEDAI versions, the SLEDAI 2K and the SELENA SLEDAI which was devised for the Safety of Estrogens in Lupus Erythematosus

National Assessment (SELENA) trial. The PGA refers to Physician's Global Assessment which is performed on a weighted 100 mm scale devised specifically for lupus designed as part of the SLEFI (SELENA SLEDAI flare index). Based on the BILAG scores at entry (A-E in each organ) the BICLA response is defined by at least one letter grade improvement in each organ without an increase in the SLEDAI score or an increase of 10% in the PGA. There must also be no off-protocol treatment in order to meet this response criteria. The primary endpoint is BICLA response rates at month 6 in the abatacept treatment group vs the placebo group. BICLA response at each month will also be assessed as a secondary endpoint.

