## 9. Statistical Considerations

**Enrollment is expected to include at least 70 screened and 60 randomized subjects** subjects have either reached a six month endpoint and/or been defined as a permanent non-responder for off protocol treatment or by dropping out of the protocol.

**The primary endpoint is the proportion of placebo vs treatment subjects who meet the primary endpoint of BICLA response using Chi Square analysis at month 6 as determined by an intent to treat analysis**

Subjects who drop out prematurely for any reason or are treated with off protocol medications or cross over to open label for lack of response at Month 3-6 are considered non responders at month 6.

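### The SF-36, LupusPRO and treat-to-target validation uses a rule-based non-responder label as its standard for clinical improvement, and the Month 9 markers have no stated clinical visit to be compared with

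*Combined protocol and SAP*

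**What the plan says.** Under Other Assessments: Optional Exploratory Analyses, the protocol proposes to measure the sensitivity and specificity of SF-36, LupusPRO and "a physician-friendly treat to target system for clinical improvement and biologic changes". It adds: "The primary clinical and biologic endpoints will be used as the standard comparators". There are therefore two references, one clinical and one biologic.

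The clinical reference is fixed in section 6.4.1: "The primary endpoint is BICLA response rates at month 6 in the abatacept treatment group vs the placebo group". The same section adds a treatment condition: "There must also be no off-protocol treatment in order to meet this response criteria". Section 9 applies the rule to "Subjects who drop out prematurely for any reason or are treated with off protocol medications or cross over to open label", and states that those who "cross over to open label for lack of response at Month 3-6 are considered non responders at month 6". Section 4.1 gives the same label to patients on off-protocol medication and to Month 3 switchers.

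These patients remain observable. Sections 4.1 and 4.2.3 keep patients who take off-protocol treatment or stop study drug early on monthly visits to Month 6. The Time and Events Schedule has BILAG, SLEDAI, PGA and the questionnaires at every visit through Month 12.

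For the markers, item 8 of section 6.4.2 plans a "Responder Analysis using the primary endpoint and assessing baseline evidence of (and changes in) a panel of markers", and section 9.4.4 also refers to the primary clinical endpoint. The primary biologic endpoint is sampled after dosing at Month 3, and then: "This will be repeated at Month 9 to include changes in placebo-treated patients after 3 months on abatacept".

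**The concern.** Setting switched and off-protocol-treated patients to non-response suits a comparison of randomised arms, where needing other treatment is itself a failure. A reference standard for improvement has a different job: it should say whether the patient was better at that visit. A patient who improved on open-label abatacept or added medication, and whose questionnaire shows it, counts against the questionnaire. Useful tools would look less specific than they are. The planned placebo response is very low and early crossover is offered, so the affected group could be sizeable.

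The marker work has a related gap. It asks whether baseline elevation or post-dose reversal predicts response to abatacept. For a placebo patient who has since started abatacept, the Month 6 label is a result on placebo or a failure imposed by rule. Neither is a response to abatacept. Section 2.2 looks to the biomarker data to help select patients for later trials, so the pairing should be settled in advance.

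**Working it through.** **Plan's scenario.** Sections 9.1 and 9.2 give 60 patients, 1:1, with 5% placebo response and 35-50% on abatacept. The power table's 40% versus 5% column states 0.86. A two-sided 0.05 test with 30 per arm, pooled null variance and continuity correction gives 0.859. This only confirms the scenario used below; the documents give no figure for the validation analyses.

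**Labelled counts at 40% versus 5%.**
- Responders: 30 × 0.40 + 30 × 0.05 = 12 + 1.5 = 13.5
- Non-responders: 60 − 13.5 = 46.5

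**Effect of the label on specificity.** Let k be the number of labelled non-responders who have in fact improved at Month 6.

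Measured specificity = [(46.5 − k) × Sp + k × (1 − Se)] / 46.5

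Assumptions, none from the documents: Sp = 0.90, Se = 0.80, 30-70% of the 30 placebo patients switch, and 20-40% of those improve.
- Low end: k = 30 × 0.30 × 0.20 = 1.8. Specificity = (44.7 × 0.90 + 1.8 × 0.20) / 46.5 = 40.59 / 46.5 = 0.87.
- High end: k = 30 × 0.70 × 0.40 = 8.4. Specificity = (38.1 × 0.90 + 8.4 × 0.20) / 46.5 = 35.97 / 46.5 = 0.77.

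Only placebo switchers are counted here; improved patients on off-protocol treatment in either arm would add to k.

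**Sensitivity to the assumptions.** With f = k / 46.5, specificity falls by f × (Se + Sp − 1). Each 10% of labelled non-responders who have truly improved costs 6 points at Se = Sp = 0.80 and 8 points at Se = Sp = 0.90. There is no bias at f = 0. The direction is fixed for any informative tool, meaning one with Se + Sp above 1.

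**Month 9 markers.** At 5% placebo response, 30 × 0.95 = 28.5 placebo patients carry a Month 6 non-responder label. Suppose all start open label and 35-50% then respond. Then 28.5 × 0.35 = 10.0 to 28.5 × 0.50 = 14.3, or about 10 to 14 patients, would have a Month 9 marker on abatacept beside a label that contradicts their current state. This applies only if the Month 6 label were used, and the plan does not say which visit is.

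**The case against.** The strongest defence is that this work is optional and exploratory, and that the protocol notes these patient-reported outcomes have not been directly compared against efficacy endpoints. Agreement with the trial's own endpoint is then part of the aim. That stands, and is a reason to keep the rule-based endpoint as a second comparator. It does not make that endpoint a measure of clinical improvement, which is what the sensitivity and specificity are said to be for.

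The size also rests on assumed rates. At the low end the shift of 0.03 is smaller than one standard error, √(0.90 × 0.10 / 46.5) = 0.044. That is correct; the bias might be minor in practice.

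Several stronger readings are tempting, and the documents do not support them:
- **That Month 9 markers are matched to Month 6 results.** No section says so. BICLA at each month is a secondary endpoint and its components are scored through Month 12, so a Month 9 comparator could be built. The gap is that the pairing is unspecified; section 9.4.4 says only that the change is measured after treatment.
- **That the marker association would be reversed.** Assume 40% true response on abatacept, marker reversal in 80% of true responders and 20% of others, all 30 placebo patients starting open label, and Month 6 labels. Pooling the arms takes the odds ratio from 16 in the abatacept arm to (10.26/3.24) / (16.14/30.36) = 6.0. That is dilution. The plan also describes a comparison by arm, not a pooled one.
- **That every rescued or dropped-out patient is mislabelled.** Protocol-allowed depomedrol through Month 2 does not trigger the rule, and a drop-out with no Month 6 assessment cannot enter the table.
- **That DIAL is being validated.** The text names only a treat-to-target system, and Exploratory Clinical Assessments lists LFA REAL.
- **That omitting Month 6 from the in-house marker timings is an error.** The plan takes Month 3 samples before non-responders start new immune suppressants, because those could confound later assays. At Month 6 that confounding is present. The ancillary studies in Appendices 3 and 6 do use Month 6 blood.

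**Conclusion.** The concern holds for the clinical comparator. Followed as written, the plan counts a correctly detected improvement in a switched or off-protocol-treated patient as a false positive, and no other reference for clinical improvement is planned. The downward bias in specificity follows from the definition; its size, 0.90 falling to between 0.87 and 0.77, rests wholly on the assumed accuracy, switching and improvement rates. Drop-outs contribute only if they keep attending. Nothing here shows bias against the biologic comparator.

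For the markers, the finding is an omission: the clinical visit paired with the Month 9 sample is not defined. Using the Month 6 label for placebo patients then on abatacept would dilute any association. The primary comparison of arms is unaffected. The point deserves correction because the remedy is cheap and the marker results are meant to inform later trials.

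**What to change.** Add the following to the analysis text for the correlative studies.

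1. As the reference for clinical improvement, use the BICLA clinical components (BILAG, SLEDAI, PGA) as observed at the same visit as the tool, without the treatment or drop-out rule. Keep the rule-based primary endpoint as a second comparator.
2. Pair Month 9 markers with Month 9 observed status. For patients who started open label, take the last visit before the first open-label dose as baseline, and report them separately from the randomised comparison.
3. State the visit meant by after treatment in section 9.4.4, and name the treat-to-target instrument.
4. Treat Month 6 runs of the primary markers as optional. If done, report them separately for patients still on randomised treatment.
5. Reconcile section 5.6.1, where starting an immune suppressant only may lead to non-responder status, with sections 4.1 and 9, where it does.

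The cost is wording and a little more analysis work. Clinical scores are already collected at every visit, and Month 6 blood is already drawn; only the optional assays would add laboratory expense.
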